18.3 Tracking study medication intake, emollient and rescue medication

Following the completion of the

will be asked to answer the following questions every evening:

Did you take your study medications (capsules) today?

🗆 No

 \Box Yes

Did you apply any emollient today?

□ No

□ Yes

Please answer ONLY in case your study doctor has provided you with a rescue cream and asked you to apply it: Did you apply the rescue cream today?

 \square No

□ Yes

# Document History – Changes compared to previous final version of SAP

Date		Reason for update	Outcome for update	Section and title impacted (Current)
29- Sep- 2020	Prior to DB lock	Creation of final version	N/A - First version	NA

# List of abbreviations

AE	Adverse event
ATC	Anatomical Therapeutic Classification
AUC	Area Under the Curve
bid	bis in diem/twice a day
CSR	Clinical Study report
CTC	Common Toxicity Criteria
CTCAE	Common Terminology Criteria for Adverse Events
DMC	Data Monitoring Committee
FAS	Full Analysis Set
eCRF	Electronic Case Report Form
IVR	Interactive Voice Response
IWR	Interactive Web Response
MedDRA	Medical Dictionary for Drug Regulatory Affairs
NCI	National Cancer Institute
o.d.	Once Daily
OS	Overall Survival
PFS	Progression-Free Survival
PPS	Per-Protocol Set
PRO	Patient-reported Outcomes
qd	Qua'que di'e / once a day
RAP	Report and Analysis Process
RECIST	Response Evaluation Criteria in Solid Tumors
SAP	Statistical Analysis Plan
SOC	System Organ Class
TCI	Topical Calcineurin Inhibitors
TCS	Topical Corticosteroids
TFLs	Tables, Figures, Listings
WHO	World Health Organization

# 1 Introduction

This Statisticial Analysis Plan (SAP) describes the statistical analysis planned for the Clinical Study Report (CSR) for studies ZPL389A2203 and ZPL389A2203E1 (henceforth called A2203 and A2203E1, respectively). Both studies will be reported in the same CSR.

Following an interim analysis with database lock in May 2020, the decision was made to stop both study A2203 (the core study) and A2203E1 (an extension study) and this SAP reflects changes to the analysis strategy described in the protocols (V3 for A2203 and V1 for A2203E1) that were made following this decison.

[figure not shown]
# 1.1 Study design

The core study (A2203) was planned as a randomized, double blind, placebo controlled, parallel group, 5-arm study in at least 360 subjects with moderate to severe Atopic Dermatitis (AD). Unbalanced randomization ratio was used, intending to result in approximately 90 subjects randomized in each of the 30 mg/day and 50 mg/day dose arms as well as in the placebo arm, and 45 subjects in each of the 3 mg/day and 10 mg/day arms. The randomization was stratified by baseline severity of atopic dermatitis (IGA score moderate or severe) and by geographical region.

The possibility to perform an interim analysis (IA) in order to support decision making concerning the current clinical study or project was addeded to the protocol in V3. This interim analysis was performed in May 2020 on 187 patients who had completed week 16 or discontinued before this timepoint. Based on the results from this IA, it was decided to stop both the core and extension studies for reasons of lack of efficacy and thus the final number of patients, and follow-up time per patient is less than planned in the protocol.

The core study (A2203) consisted of a screening period of up to 4 weeks (depending on current medication use and associated washout period), and a 16-week double blinded treatment period. The primary endpoint was to be assessed at the end of the 16 week treatment period.

After the end of treatment visit, subjects were offered the possibility of ongoing treatment in the extension study (A2203E1), or of entering the 4 week treatment-free follow up period.

[figure not shown]

The extension study (A2203E1) was intended to be a randomized, double blind, parallel group, 2-arm study in up to approximately 202 to 230 subjects. This number assumed a discontinuation rate of 15% to 25% in the core study (A2203)

In the extension study, subjects who had received ZPL389 30 mg o.d. or 50 mg o.d. doses in the core study, would continue to receive the same doses in a double-blinded fashion. Subjects who had received ZPL389 3 mg, 10 mg or placebo in the core study, would be randomized to receive ZPL389 30 mg o.d. or 50 mg o.d. in a 1:1 ratio. All subjects would receive concomitant or intermittent topical corticosteroids (TCS) and/or topical calcineurin inhibitors (TCI) along in a standardized regimen with ZPL389.

After completing 100 weeks of study treatment during the extension study (i.e. up to Week 116 including 16 weeks of the core study), subjects were to enter the 4 weeks treatment-free follow-up period.

# 1.2 Study objectives and endpoints

Following the decision to stop the studies, not all will be evaluated in the abbreviated CSR, as indicated in the table below.

Table 1-1 Ob	jectives for the core	study A2203
--------------	-----------------------	-------------

Objective	Endpoint	Included in CSR?
Primary objective		
To characterize the dose- response relationship of ZPL389 in subjects with moderate to severe AD assessed by IGA response after 16 weeks of treatment	IGA response at Week 16	Yes
Secondary objectives		

Novartis SAP

Objective	Endpoint	Included in CSR?
To characterize the dose- response relationship of ZPL389 in subjects with moderate to severe AD assessed using the percent change from Baseline in Eczema Area and Severity Index (EASI) score after 16 weeks of treatment	Percent change from baseline EASI score at Week 16	Yes
To evaluate the efficacy across different dose levels as assessed by EASI and IGA compared to placebo over time	At each visit: IGA score IGA response EASI score (absolute and percent change from Baseline) EASI50 response, EASI75 response	Yes (except IGA score and absolute change in EASI score from baseline)
To assess the safety and tolerability of different doses of ZPL389 as compared to placebo	Frequency of adverse events	Yes

Novartis	For business use only	Page 10
SAP		CZPL389A2203

Objective	Endpoint	Included in CSR?

# Table 1-2Objectives for the extension study A2203E1

Objectives	Endpoints

[figure not shown]
Included in CSR?

Primary objective

Novartis F	or business use only
SAP	

Page 11 CZPL389A2203

Objectives	Endpoints	Included in CSR?
To assess the short-term and long- term safety of 30 mg o.d and 50 mg o.d ZPL389 with concomitant or intermittent use of TCS and/or TCI up to total of 32 weeks and 116 weeks of treatment.	Frequency of AEs at Week 32 (short- term) and Week 116 (long-term).	Yes
Secondary objectives		
To evaluate the efficacy of 30 mg o.d and 50 mg o.d ZPL389 with concomitant or intermittent use of TCS and/or TCI as assessed by IGA response over time.	IGA score over time (absolute and relative frequencies from core study baseline).	Yes
To evaluate the efficacy of 30 mg o.d and 50 mg o.d ZPL389 with concomitant or intermittent use of TCS and/or TCI as assessed by EASI	EASI score over time (absolute and percent change from core study baseline).	Yes

Novartis SAP	For business use only	Page 12 CZPL389A2203
Objectives	Endpoints	Included in CSR?

# 2 Statistical methods

# 2.1 Data analysis general information

Novartis will perform the analyses for this study. Statistical software SAS verion 9.4 or later will be used.

All available data from the core and extension studies will be presented together.

Where summary statistics are presented these will include, for continuous variables N, mean, standard deviation, minimum, and maximum, and for discrete variables, counts and appropriate percentages.

If not otherwise specified, p-values will be presented for two-sided hypothesis testing, twosided confidence intervals will be displayed and the level of significance will be set to 5% twosided.

In general listings will be presented by treatment sequence showing the sequence of treatments in the core and extension study, i.e as follows and in this order

- Placebo did not participate in extension
- Placebo ZPL389 50mg
- Placebo ZPL389 30mg

- ZPL389 3mg did not participate in extension
- ZPL389 3mg ZPL389 30mg
- ZPL389 3mg ZPL389 50mg
- ZPL389 10mg did not participate in extension
- ZPL389 10mg ZPL389 30mg
- ZPL389 10 mg ZPL389 50mg
- ZPL389 30mg did not participate in extension
- ZPL389 30mg ZPL389 30mg
- ZPL389 50mg did not participate in extension
- ZPL389 50mg ZPL389 50mg

# 2.1.1 General definitions

Study treatment is either placebo or 3, 10, 30 or 50mg ZPL389.

Day 1 is defined to be the first day of administration of any study treatment.

All other study days will be labeled relative to Day 1. For event dates on or after Day 1, studyday for a particular event date is calculated as [Date of event] – [Date of first dose]+1, i.e., Day 2, Day 3, etc., will be one day, two days, etc., after Day 1, respectively. For the dates beforeDay 1, study day for an event date is calculated as [Date of event] – [Date of first dose], i.e., Day - 1, Day -2, etc., will be one day, two days, etc., before Day 1, respectively. Duration of an event will be calculated as (Event end date – Event start date + 1).

The descriptor "Day 0" will not be used.

Screening refers to any procedure (e.g., checking inclusion and exclusion criteria) performed prior to the date of first dose of study treatment. Per protocol, subject informed consent must be obtained prior to performing any study related activity. The date of signing informed consent is the start date of screening period.

Baseline is considered to be the last assessment (including those from unscheduled visits) obtained before the first dose of study treatment. All assessments obtained after first dose of study treatment are considered as post-baseline unless otherwise specified.

In general, a baseline value refers to the last measurement made prior to administration of the first dose of study treatment. However, if no pre-treatment value exists, values obtained after first dose of treatment but on that same day of dosing will be considered as the baseline.

The date of last dose will be collected via the CRF. The end of the treatment period will be defined as the last dose date or last visit in treatment period whichever occurs earlier. i.e., for subjects who discontinued or have their last visit earlier than last dose date, the end of study treatment will be the date of the last study visit in the corresponding treatment period.

The core study treatment period is defined to be the time up until the date of the first visit in the extension study whilst the patient is receiving study treatment.

The extension study treatment period is defined to be the time up from the first visit in the extension study until the end of study treatment

The follow-up period is defined to be the time from last dose of study treatment until the end of the study (latest of core and extension for that patient).

The concept of assessment windows will be used for the data that is summarized by visit. Each assessment window is based on the study evaluation schedule and comprises a set of days around the nominal visit day. For any assessment, there are the protocol defined scheduled visits around which windows were created to cover the complete range of days within the study. The visit windows are shown in Table 2-1.

These assessment windows apply to measurements taken at every visit. For assessments which are not collected at every visit, the assessment windows defined in Table 2-1 will be combined. For example, if an assessment is measured at Week 4 and Week 8 only, the Week 4 assessment window for this parameter will extend from Day 2 to Day 43 (combining Week 2 to Week 4), Week 8 will extend from Day 44 to Day 71 (combining Week 6 to Week 8).

When assessment windows are used, all visits will be re-aligned, i.e., they will be mapped into one of the assessment windows. For example, if the Week 4 visit of a subject is delayed and occurs on Day 60 instead of on Day 29, the data will be considered to relate to Week 8. In the case of major deviations from the visit schedule, or due to unscheduled visits, several assessments of a subject may fall in a particular assessment window (either scheduled or unscheduled). The approaches to handle multiple assessments in a given window are specified below.

Assignment of data to the assessment windows will be done before deriving further parameters (e.g. change from baseline, responder status) from the assessments. The assessment windows will be used for summary tables and figures but listings will show the original visit at which the data were recorded, along with the study day of the assessment.

I able 2-1			
Visit as used for reporting	Week	Scheduled study day	Assessment window
Screening	SCN	-35 to -1	Day -35 to -1
Baseline	0	1	Day 1
Week 2	2	15	Day 2 – 22
Week 4	4	29	Day 23 – 26
Week 6	6	43	Day 37 – 50
Week 8	8	57	Day 51 – 71
Week 12	12	85	Day 72 – 99
Week 16	16	113	Day 100 – 127
Week 20	20	141	Day 128 – 155
Week 28	28	197	Day 184-211
Week 32	32	225	Day 212-267
Week 44	44	309	Day 268-351
Week 56	56	393	Day 352-435
Week 68	68	477	Day 436-519
Week 80	80	561	Day 520-603
Week 92	92	645	Day 604-687

Table 2-1Visit windows

Novartis For business use only SAP		Page 15 CZPL389A2203	
Visit as used for reporting	Week	Scheduled study day	Assessment window
Week 104	104	729	Day 688-771
Week 116	116	8130	Day 772-827
Week 120	120	841	Dav >= 828

If more than one assessment falls into the interval, the rules defined below will be applied unless otherwise specified.

- for quantitative variables, the closest to the actual visit is chosen (if two assessments have the same distance, then the earlier one will be chosen);
- for qualitative variables, the worst record is selected.

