If discontinuation of study treatment occurs, the subject should not receive additional doses. Subjects should remain in the study and be followed at least until the adverse event resolves / stabilizes, or until the end of the study, whichever is longer. I.e. After study treatment discontinuation, the subject should remain in the study and attend study visits as normal in Table 6-1 (without contacting IRT /drug dispensing). Subjects who discontinue treatment and wish to discontinue the study should at a minimum return for the End of Treatment visit (Week 16 visit) and the Follow up visit (Week 20 visit), as detailed in Table 6-1, and assessment should be completed and recorded in the appropriate CRF. The investigator must determine the primary reason for the subject's premature discontinuation of study treatment and record this information on the CRF.

The investigator must also contact the IRT to register the subject's discontinuation from study treatment.

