#### Concomitant medication

Concomitant medications are defined as drugs taken at least once between start and end of study treatment (inclusive)

Concomitant treatments will be displayed for:

- the core study treatment period by the relevant treatment group for that period,
- the extension study treatment period by the relevant treatment group for that period

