## Handling of remaining intercurrent events:

- Treatment discontinuations for lack of efficacy or adverse event: consider as non-responder
- Treatment discontinuations for any other reason: set data after discontinuation to be missing

The summary measure: difference in response rates between ZPL389 and placebo.

This estimand differs from that intended by the protocol in that the definition of the endpoint of IGA response has changed to include any use of confounding medication as a non-response, rather than only confounding medication that was adjudicated as having an effect on the IGA response, as specified in the protocol. This change was made following the interim analysis where it was established that handling use of confounding medication did not affect the overall conclusions and so it was decided not to perform the adjudication.

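### SAP 2.1.1 dates the end of study treatment inconsistently: some extension days on drug fall in no period, and some medications count as neither or both of concomitant and follow-up

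*SAP*

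**What the plan says.** SAP 2.1.1 says three things about when treatment stops.

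- The rule: "The end of the treatment period will be defined as the last dose date or last visit in treatment period whichever occurs earlier".
- The sentence that explains it, introduced by i.e., covers a wider group: "for subjects who discontinued or have their last visit earlier than last dose date, the end of study treatment will be the date" of a visit, not of a dose. In full, "the end of study treatment will be the date of the last study visit in the corresponding treatment period".
- Follow-up: "The follow-up period is defined to be the time from last dose of study treatment until the end of the study".

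The same section defines the two treatment periods separately. The core period runs up to the first extension visit, but only for time on study drug. The extension period runs from that visit to the end of study treatment, with no on-drug condition.

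The date is used elsewhere. SAP 2.4.2 says "Concomitant medications are defined as drugs taken at least once between start and end of study treatment (inclusive"), whereas its follow-up medications are those begun after the last dose. SAP 5.1.2 caps incomplete medication end dates at the treatment end date. For patients who stop drug early, Protocol 5.6.2 says that "the subject should remain in the study and attend study visits as normal in Table 6-1", and the treatment columns of that table run to Day 113.

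**The concern.** The end of treatment and the start of follow-up should be adjacent. Here one can be a visit date while the other is always a dose date, so the two can be separated or can overlap. The SAP itself foresees a last visit before the last dose, so the separation is not a contrived case. The overlap arises if the explanatory sentence is taken at its word for discontinuers, because the protocol keeps them on the visit schedule after their last dose.

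At stake are the end of the extension treatment period, the split between concomitant and follow-up medication, and the imputed end dates of medications. There may be a further consequence. SAP 2.1.1 identifies prohibited, and hence confounding, therapy from concomitant medications in listed drug classes. If concomitant there carries its 2.4.2 meaning, the end date also helps decide who fails the no-confounding-therapy condition in IGA response.

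**Working it through.** The plan gives no figure here to reproduce. The check is to apply its sentences to example timelines.

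**Inputs.** Days 85 and 113 are scheduled visits in Protocol Table 6-1. Day 225 (Week 32) is a scheduled visit in SAP Table 2-1, where the next is Day 309 (Week 44), 309 − 225 = 84 days later. The completer takes the last dose on Day 112, the day before the Day 113 visit. The other last-dose days are illustrative assumptions.

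**Rules.** Let D be the last dose day and V the last visit day.

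- Earlier-of rule: E1 = min(D, V).
- Explanatory sentence, literal reading, with Table 6-1's treatment columns taken as the treatment period: E2 = V if the patient discontinued or if V < D; otherwise E1.
- Follow-up starts on D.
- Off-drug days up to the end of treatment = max(0, E2 − D).
- Days after the end of treatment and before follow-up = max(0, D − E − 1), where E is E1 or E2; the two agree in both rows where this count is above zero.

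| Timeline | D | V | E1 | E2 | Off-drug days up to E2 | Days between E and follow-up |
|---|---|---|---|---|---|---|
| Core completer | 112 | 113 | 112 | 112 | 0 | 0 |
| Stops early, attends to Day 113 | 30 | 113 | 30 | 113 | 113 − 30 = 83 | 0 |
| Stops later, attends to Day 113 | 60 | 113 | 60 | 113 | 113 − 60 = 53 | 0 |
| Core, last seen before last dose | 98 | 85 | 85 | 85 | 0 | 98 − 85 − 1 = 12 |
| Extension, last seen before last dose | 281 | 225 | 225 | 225 | 0 | 281 − 225 − 1 = 55 |

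**Periods.** In the extension row, Days 226 to 280 are on drug but lie in neither the extension treatment period nor follow-up. In the core row, the separate core definition keeps the 12 days inside the core treatment period because the patient is still on drug.

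**Medications.** A follow-up medication must start after D, so the interval that satisfies neither 2.4.2 definition is D − E days. That is 281 − 225 = 56 days (226 to 281) in the extension row and 98 − 85 = 13 days (86 to 98) in the core row. In the Day 30 row, on the literal reading, a medication first taken on Days 31 to 113 is used before the end of treatment and begun after the last dose, so it meets both definitions.

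**With one date.** Setting E = D for everyone, with follow-up from D + 1, makes both counts zero in every row and leaves no medication in neither class or in both.

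**The case against.** The best defence has four parts.

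1. *The core period has its own definition.* This is right. A reader might infer that on-drug core days after a last visit belong to no period, or that off-drug days count as core treatment. The on-drug condition rules out both. It does not reach the extension period. Nor does it change the 2.4.2 definition of concomitant medication, which is bounded by the end of study treatment, although the core display by treatment period sits awkwardly with that bound.

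2. *The explanatory sentence illustrates the rule and does not replace it.* The condition about the last visit preceding the last dose may qualify discontinuers too, or discontinued may mean leaving the study. Either reading removes the overlap. If the discontinuation visit, placed by Table 6-1 on the day after the last dose, is the last treatment-period visit, the difference is about one day. So the 83-day figure depends on one reading among several. None of these readings closes the gap when the last visit comes first.

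3. *The primary estimand does not cite this date.* A reader might infer that an off-drug Week 16 score could be kept as an observed response, diluting the treatment effect. The documents do not support that. SAP 2.5.1 says "Treatment discontinuations for any other reason: set data after discontinuation to be missing", without reference to the end-of-treatment date. The protocol glossary and Protocol 5.6.2 define treatment discontinuation as stopping drug, and the last dose date is on the CRF. A patient who stops on Day 30 has discontinued on Day 30.

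4. *The confounding-therapy flag is only loosely tied to the date.* Rescue use comes from its own CRF page with no end-of-treatment limit. Nothing says the 2.4.2 reporting split governs prohibited medications, and a patient lost after the last visit may have no later medication recorded. This leaves an effect possible but not shown.

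Exposure duration in SAP 2.4.1 and the treatment-emergent cut-off in SAP 2.7.1 both use the last dose or intake, so they are untouched.

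**Conclusion.** The inconsistency is real and limited in reach. What holds on every reading of the explanatory sentence is the gap: when the last visit precedes the last dose, on-drug days fall outside the extension treatment period, and a medication first taken then is neither concomitant nor follow-up. In the extension example this is 55 days and 56 days respectively. What holds only on the literal reading is the overlap, 83 or 53 days in the examples, in which a medication counts as both.

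These are lengths for assumed timelines, not estimates for the trial. A reader might want the number of patients affected or the dilution of the planned 20-point effect. Neither can be derived: the final sample size is not given beyond being below 360, the number with these date patterns is not stated, and dilution would need off-drug scores to be kept, which 2.5.1 does not say. The interim analysis showed no treatment effect, so the overall efficacy conclusion is unlikely to turn on this. It remains worth correcting, because medication tables and period assignments would otherwise rest on an unstated programming choice.

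**What to change.** In SAP 2.1.1, remove the earlier-of condition and the explanatory sentence, and define the end of study treatment as the CRF last dose date for every subject. Start follow-up on the day after. Use this date for the end of the extension treatment period, for the concomitant/follow-up split in 2.4.2 and for the medication end-date imputation in 5.1.2. Leave the core period definition as it is.

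State also that this is the discontinuation date wherever later data are set to missing (2.5.1, 2.5.4, 2.6.2, 2.6.5 and 2.6.6). Because the discontinuation visit falls a day later, say whether that assessment is kept; this is an estimand choice for the SAP authors. One further sentence should say whether concomitant in the confounding-medication paragraph has its 2.4.2 meaning.

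The cost is a few sentences and the matching programming. The last dose date is already collected, and the SAP is dated before database lock.

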#### **Endpoints:**

IGA response at each week after week 16, where IGA response is defined as an IGA score of 0 or 1 with at least a 2 point improvement compared to baseline.

Percentage change from baseline in EASI at each week after week 16

EASI50 response at each week, where EASI50 response is defined as a reduction from baseline of  $\geq$  50% in EASI score.

EASI75 response at each week, where EASI75 response is defined as a reduction from baseline of  $\geq$  75% in EASI score.

Change from baseline in peak pruritus score at each week after week 16

**Treatment of interest:** the randomized treatment (ZPL389 or placebo) plus medications as allowed by the protocol including TCS or TCI and including rescue medication but with no further treatment for patients who discontinue study treatment due an AE or lack of efficacy.

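### As printed, SAP Table 2-1 gives Days 156-183 no visit window, although SAP 2.1.1 says the windows cover every study day

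*SAP*

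**What the plan says.** SAP 2.1.1 (General definitions) sets assessment windows for data summarised by visit. It says that "windows were created to cover the complete range of days within the study" and that "all visits will be re-aligned, i.e., they will be mapped into one of the assessment windows". On sequence, "Assignment of data to the assessment windows will be done before deriving further parameters", with change from baseline and responder status given as examples of what is derived afterwards. On scope, "The assessment windows will be used for summary tables and figures but listings will show the original visit at which the data were recorded".

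Table 2-1 gives Week 20 (scheduled Day 141) the window Days 128-155. The next row is Week 28 (scheduled Day 197), with Days 184-211.

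SAP 2.6.6 lists the efficacy endpoints after Week 16, among them "IGA response at each week after week 16", EASI percent change, EASI50 and EASI75 response, and change in peak pruritus score. Under SAP 2.6.7 and 2.6.8, continuous endpoints are analysed by MMRM with visit as a factor and are not imputed. Missing binary responses are imputed from scores at all visits up to the time point concerned.

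**The concern.** The text promises complete coverage, and the table does not deliver it. An assessment on Days 156-183 cannot be mapped as the text requires. The rules that follow Table 2-1 deal only with several assessments in one window and say nothing about an assessment in none.

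Because windowing comes before the endpoints are derived, an unmapped score has no visit label. Taken literally, it contributes to no by-visit extension estimate, cannot enter an MMRM that needs a visit level, and is not there to inform imputation of a later binary response. The alternative is that a programmer decides case by case, without documentation. A SAP finalised before database lock should leave neither option open.

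The studies were stopped early and follow-up was shortened. The early extension visits, next to this gap, are therefore likely to hold a good part of the extension data, although the documents give no counts.

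**Working it through.** **Inputs.** Scheduled days and windows come from SAP Table 2-1. The Week 116 scheduled day appears as 8130 and is read here as 813 = 116×7+1.

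**Step 1: coverage.** Week 20 ends on Day 155 and Week 28 begins on Day 184. The uncovered days are 156 to 183, that is 183 − 156 + 1 = 28 days. The stated complete coverage is not reproduced.

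**Step 2: how the table sets its bounds.** The SAP states no formula, so this tests whether each upper bound is the midpoint of adjacent scheduled days.

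| Boundary | Midpoint | Printed upper / next lower | Match |
|---|---|---|---|
| Week 12/16 | (85+113)/2 = 99 | 99 / 100 | yes |
| Week 16/20 | (113+141)/2 = 127 | 127 / 128 | yes |
| Week 20/28 | (141+197)/2 = 169 | 155 / 184 | **no** |
| Week 28/32 | (197+225)/2 = 211 | 211 / 212 | yes |
| Week 32/44 | (225+309)/2 = 267 | 267 / 268 | yes |
| Week 44/56 | (309+393)/2 = 351 | 351 / 352 | yes |
| Week 56/68 | (393+477)/2 = 435 | 435 / 436 | yes |
| Week 68/80 | (477+561)/2 = 519 | 519 / 520 | yes |
| Week 80/92 | (561+645)/2 = 603 | 603 / 604 | yes |
| Week 92/104 | (645+729)/2 = 687 | 687 / 688 | yes |
| Week 104/116 | (729+813)/2 = 771 | 771 / 772 | yes |
| Week 116/120 | (813+841)/2 = 827 | 827 / 828 | yes |

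From Week 12 onward, Week 20/28 is the only failure. Before Week 12 there is one other: Week 4/6 has midpoint 36 but is printed as 26, which leaves Days 27-36 uncovered. That is a separate error in the core study, and correcting it does not close this gap.

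**Step 3: what would explain 155 and 184.** Put a Week 24 visit at Day 24×7+1 = 169. Then (141+169)/2 = 155 and (169+197)/2 = 183, so the next window starts on Day 184. Both printed bounds are reproduced and the implied row covers exactly Days 156-183.

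**Step 4: if there was no Week 24 visit.** The same pattern puts the single boundary at Day 169, giving Week 20 = Days 128-169 and Week 28 = Days 170-211. The printed bounds would then depart from the pattern on both sides. The table therefore needs correcting on either reading.

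**The case against.** The strongest reply is that the omitted row is an inference. The extension has its own protocol, which is not among the documents, and the SAP states no midpoint rule. The windows for Weeks 12, 16, 20 and 28 also fit a fixed span of 13 days before to 14 days after the scheduled day. This stands as far as the existence of a Week 24 visit goes. It does not rescue the table. The fixed-span reading fails at Week 32 (225 + 14 = 239, printed 267) and still leaves Days 156-183 uncovered.

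Without a Week 24 visit the practical effect would be small. The gap starts 15 days after the Week 20 day (156 − 141) and ends 14 days before the Week 28 day (197 − 183), so only badly mistimed or unscheduled visits would fall in it. That stands.

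A row lost in conversion of the PDF to text cannot be fully excluded, given the 8130 in the same table. There is no redaction mark or page break at that point, and the PDF will settle it.

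The combining rule might be thought to bridge the gap: "For assessments which are not collected at every visit, the assessment windows defined in Table 2-1 will be combined". It is confined to such assessments and does not help one scheduled at every visit.

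A reader might also infer that all data from these days are discarded. The SAP does not say so. It says that all visits are mapped, which its own table makes impossible here. Nor would EASI percent change be imputed, since SAP 2.6.8 leaves missing continuous values to the MMRM.

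**Conclusion.** The point holds as an internal contradiction: 28 consecutive days have no window in a table said to cover them all, and no rule says what to do with assessments made then. The loss from by-visit extension efficacy follows only if the table is applied literally.

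The 28 days are 28/112 = 25% of the calendar time from Week 16 (Day 113) to Week 32 (Day 225). A reader might take that as a quarter of the early extension data. The documents do not support this, because they give no count of assessments or subjects in the period.

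The Week 16 primary and secondary analyses, the adverse event summaries by onset date (the basis of the extension's primary objective) and the listings, which keep the original visit and study day, are all untouched. The extension had no placebo arm and the programme stopped for lack of efficacy, so nothing here suggests that the trial's conclusion would change. It remains a wrong specification that should be corrected.

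The conclusion about coverage rests on the table as printed. The attribution to a missing Week 24 row rests also on the inferred midpoint pattern and on reading the Week 116 day as 813.

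**What to change.** Check the extension visit schedule, and the PDF of Table 2-1, for a Week 24 visit.

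- If it exists, insert `Week 24 | 24 | 169 | Day 156-183`.
- If it does not, set Week 20 to Day 128-169 and Week 28 to Day 170-211.

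Then re-run the windowing program and the by-visit outputs after Week 16. A sentence saying how an assessment outside every window is handled would be a useful addition. The Week 4 upper bound needs its own correction.

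The cost is one row or two bounds in a table and a re-run. No new data are needed and no Week 16 result changes.
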